14.1.36 Incomplete dates for last known date patient alive or death

All dates must be completed with day, month and year. If the day is missing, the 15th of the month will be used for incomplete death dates or dates of last contact.

14.1.37 Non-target lesion response

If no non-target lesions are identified at baseline (and therefore not followed throughout the study), the non-target lesion response at each assessment will be considered ‘not applicable (NA)’.

14.1.38 Study/project specific programming

The standard analysis programs need to be adapted for each study/project.

14.1.39 Censoring reason

In order to summarize the various reasons for censoring, the following categories will be calculated for each time to event variable based on the treatment completion page, the study evaluation completion page and the survival page.

For survival the following censoring reasons are possible:

- Alive
- Lost to follow-up

For PFS and TTP (and therefore duration of responses) the following censoring reasons are possible:

- Ongoing without event
- Lost to follow-up
- Withdraw consent
- Adequate assessment no longer available*
- Event documented after two or more missing tumor assessments (optional, see [Table 14-5](#))
- Death due to reason other than underlying cancer (*only used for TTP and duration of response*)
- Initiation of new anti-cancer therapy

*Adequate assessment is defined in [Section 14.1.25](#). This reason is applicable when adequate evaluations are missing for a specified period prior to data cut-off (or prior to any other censoring reason) corresponding to the unavailability of two or more planned tumor assessments prior to the cut-off date. The following clarifications concerning this reason should also be noted:

- This may be when there has been a definite decision to stop evaluation (e.g. reason="Sponsor decision" on study evaluation completion page), when patients are not followed for progression after treatment completion or when only UNK assessments are available just prior to data cut-off).
- The reason "Adequate assessment no longer available" also prevails in situations when another censoring reason (e.g. withdrawal of consent, loss to follow-up or alternative anti-cancer therapy) has occurred more than the specified period following the last adequate assessment.
- This reason will also be used to censor in case of no baseline assessment.

Final Version 3.0	May 12, 2021	1. Updated PFS censoring rules; 2. Added imputation rules regarding dates of death in Section 5.4.2.4.1 3. Added Section 5.5.5 Additional Analysis for Assessment the Impact of COVID-19 4. Added imputation rules on the end date of administration in Section 5.4.1 5. In Section 5.4.2, added the description of "In the causality assessment between the investigational drug and the adverse event, if the result is missing or unknown, that AE will be assessed as "suspected to be related to the investigational drug" " 6. The Chinese name of "progressive pancreatic neuroendocrine tumor" was unified throughout the document	Final Version 2.0
Final Version 3.1	October 11, 2023	1. Based on Novartis SOP requirements, the definitions of full analysis set and safety set were updated to align with the protocol	Final Version 3.0
Final Version 3.2	April 12, 2024	1. Section 5.4.2, updated the determination principle of the period to which adverse events fall into 2. Section 5.3.5, added imputation rules for start date and end date of concomitant drugs 3. Section 5.4.2.4.1, added last known alive date definition. 4. Section 5.5.2, added the definition of new anticancer therapy 5. Update case 5 of the censoring rules for PFS in Table 2, the censoring date of new anticancer therapy was adjusted from "date of last adequate tumor assessment prior to initiation of subsequent anticancer therapy" to	Final Version 3.1

Final Version 4.0	May 13, 2024	“date of last adequate tumor assessment prior to initiation of subsequent anticancer therapy (start date of the study treatment if there is no post-baseline imaging examination)”. Finalized Version	Final Version 3.2
-------------------	--------------	--	-------------------

Table of contents

Abbreviations	7
1 Project Introduction	8
2 Study objectives and study endpoints.....	8
2.1 Primary study objective	8
2.2 Secondary study objective	8
2.3 Primary study endpoints	8
2.4 Secondary study endpoints	8
3 Study design	8
4 Sample size calculation	9
5 Statistical Analysis	9
5.1 General Principle	9
5.1.1 Visit Window	9
5.2 Analysis Population	10
5.3 Study Participants	10
5.3.1 Patient Distribution	10
5.3.2 Protocol Violations	11
5.3.3 Demographic and Baseline Characteristics.....	11
5.3.4 Medical History.....	11
5.3.5 Concomitant medications.....	12
5.4 Safety Analysis (Primary Analysis)	13
5.4.1 Drug administration	13
5.4.2 Adverse events (AEs).....	13
5.4.2.1 Overview of adverse events	15
5.4.2.2 All treatment-emergent adverse events.....	15
5.4.2.3 Adverse events of special interest	16
5.4.2.4 Death, SAE and other significant AE	17
5.4.3 Laboratory tests.....	19
5.4.4 Vital signs	20
5.4.5 Other safety measurements	20
5.5 Efficacy analyses (secondary analyses).....	20
5.5.1 Overall Survival (OS)	20
5.5.2 Progression-Free Survival (PFS)	21
5.5.3 Overall response assessment	22
5.5.4 Tumor assessment	22
5.5.5 Additional analysis for assessment the impact of COVID-19	22

6	Interim analysis	23
7	Modification of the Analytical Method for the Protocol Plan.....	23
8	Statistical Analysis Form Template Statistics	23
9	Reference	23
10	Appendix	24
	Appendix 1 Visit Evaluation Schedule.....	24

Abbreviations

AE	Adverse event
ATC	Anatomical therapeutic chemical
CR	Complete response
CRF	Case Report/Record Form; the term CRF can be applied to either EDC or Paper
CTCAE	Common Terminology Criteria for Adverse Events
FAS	Full Analysis Set
MedDRA	Medical Dictionary for Regulatory Activities
OS	Overall survival
PD	Progression of disease
PFS	Progression-free survival
pNET	Pancreatic neuroendocrine tumors
PR	Partial response
PT	Preferred Term
RECIST	Response Evaluation Criteria in Solid Tumors
SAE	Serious Adverse Event
SAF	Safety Set
SAP	Statistical Analysis Plan
SD	Stable Disease
SMQ	Standard MedDRA query
SOC	System organ class
WHO	World Health Organization

1 Project Introduction

The Statistical Analysis Plan (SAP) provides and describes the statistical analysis methods and data processing principles for the Phase IV clinical study (protocol number: CRAD001PCN31) sponsored by Novartis Pharma AG to analyze and report on the efficacy and safety of this study. This SAP was formulated based on the revised clinical study protocol of version 01 (version date: May 31, 2017).

2 Study objectives and study endpoints

2.1 Primary study objective

- To evaluate the safety of treatment with Afinitor in Chinese adult patients with well differentiated progressive pancreatic neuroendocrine tumors (pNET).

2.2 Secondary study objective

- To evaluate the overall efficacy of treatment with Afinitor in Chinese patients with well differentiated progressive pNET.

2.3 Primary study endpoints

- Incidences of adverse events (AEs), AEs suspected to be related to Afinitor, Grade 3 or 4 AEs and serious adverse events (SAEs);
- AEs of special interest: Non-infectious pneumonitis.
- Other safety endpoints.

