10.8 Sample size calculation

Based on pre-marketing field survey, each year, approximately 6 to 10 patients per site will be newly diagnosed as 'locally advanced, unresectable or metastatic, well differentiated progressive pNET', about 10% to 20% of diagnosed patients will be eligible and agree to participate the study. In order to speed up the enrollment, 5 major sites, where most patients are usually referred to, are selected. Approximately 30 patients were planned in the original protocol based on feasibility. Based on further evaluation after communication with CDE, the sample size was increased to approximately 60 patients to support license renewal. Due to the uncertainties during the enrollment, the actual number of patients may differ from estimations.

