2.4 Secondary study endpoints

- Overall Survival (OS): defined as time from the start of study treatment to death due to any cause;
- Progression Free Survival (PFS): defined as time from the start of study treatment to progression or death due to any cause.

3 Study design

This is an open-label, multi-center, single-arm study of the safety and efficacy of Afinitor in adult patients with locally advanced, well differentiated progressive pNET in China.

Patient who are eligible will be provided with everolimus by sponsor to treat pancreatic neuroendocrine tumors and will follow the visit schedule in Appendix 1 Visit Evaluation Schedule to collect safety and efficacy data until disease progression, unacceptable toxicity, death, visit deviation or other reason that may lead to discontinuation before the end of study.

All patients will be followed-up for survival status every 6 months by the investigator until death, lost to follow-up, withdrawal of consent for survival or end of study.

4 Sample size calculation

The sample size was determined based on feasibility rather than statistical considerations.

Based on pre-marketing field survey, each year, approximately 6 to 10 patients at each of the 5 to 10 study sites selected for this study will be newly diagnosed as ‘locally advanced or metastatic, well differentiated pancreatic neuroendocrine tumor’, about 10% to 20% of diagnosed patients will be eligible and agree to participate the study. Approximately 30 patients were initially planned to be enrolled, and approximately 60 patients are now planned to be enrolled after further communication with the Center for Drug Evaluation. Due to the uncertainties during the enrollment, the actual number of patients may differ from estimations.

5 Statistical Analysis

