5.1 General Principle

All statistical analysis were done by using SAS 9.4 or updated version.

In general, continuous variables were descriptively summarized using number of subjects, mean, median, SD, minimum and maximum. Categorical variables and rank variables were descriptively summarized using the frequency and percentage under each category or rank. Unless otherwise specified, missing data were not included for the calculation of percentage.

The analytical method of this study was predominantly descriptive, without predetermined hypothesis test regarding the comparison of various observation periods.

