5.4.1 Drug administration

Duration of study treatment exposure, cumulative dose, dose intensity, and relative dose intensity were summarized descriptively. Where:

- Dose intensity (mg/day) = cumulative dose (mg) / duration of exposure (days), where duration of exposure (days) = time of last dose of Afinitor – time of first dose of Afinitor + 1.
- Relative dose intensity (%) = dose intensity / planned daily dose (10 mg/day) × 100%.

Patients with a certain duration of exposure (< 12 weeks, 12 - < 24 weeks, 24 - < 36 weeks, 36 - < 48 weeks, 48 - < 60 weeks, 60 - < 72 weeks, 72 - < 84 weeks, and ≥ 84 weeks) were summarized; patients with certain relative dose intensity (0 - < 50%, 50% - < 70%, 70% - < 90%, 90% - < 110%, and ≥ 110%) were summarized.

In addition, the number and percentage of patients with dose adjustments/dose interruptions (1 and ≥ 2) were summarized, and the reasons for dose adjustments were summarized by number and percentage of patients.

If the end date is missing, the following rules are used to impute:

- Missing days only: if the year and month are the same as the last visit, the date of the last visit will be used, otherwise it will be imputed with the last day of that month
- Missing month and day: if the year is the same as the last visit, the date and month of the last visit will be used, otherwise it will be imputed as December 31. If the imputed date is later than the withdrawal date, the end-of-medication date is adjusted to withdrawal date - 1 day.
- If all year, month and day are missing, it will be imputed directly with the date of the last visit

Drug administration was tabulated by patient.

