5.4.2.1 Overview of adverse events

The overview of adverse events included the number and percentage of patients with the following AE (reported by all grades and Grade 3/4, respectively):

- All death events
- Treatment-emergent deaths (all grades only reported)
- Treatment-emergent AE
- AE suspected to be related to the study drug
- Treatment-emergent SAE
- SAE suspected to be related to the study drug
- AE leading to discontinuation of medication
- AE leading to discontinuation of medication, suspected to be related to the study drug
- Other significant treatment-emergent AE (AE leading to interruption or change in dose or frequency of Afinitor, AE requiring additional treatment)

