5.5.1 Overall Survival (OS)

Overall survival is defined as time from study treatment to death due to any cause.

If a patient was alive at the data cutoff, the last known survival date was used as the censored date for analysis. The definition of the last known survival date is detailed in Section 5.4.2.4.1.

If the data permits, the Kaplan-Meier method was used to obtain the survival function estimate and the median OS estimate, the survival curve was plotted, and the error of the survival function was estimated using the Greenwood formula [1], resulting in a 95% confidence interval

of the median OS. In addition, the survival probabilities and their 95% confidence intervals at different time points such as at Month 3 and Month 6 were also calculated.

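### Adverse event incidence is the primary endpoint in about 60 patients, yet the SAP reports it only as n (%), while OS and PFS, both secondary, get 95% intervals

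*SAP*

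**What the plan says.** **Primary endpoint.** SAP 2.3 lists "Incidences of adverse events (AEs), AEs suspected to be related to Afinitor, Grade 3 or 4 AEs and serious adverse events (SAEs", then non-infectious pneumonitis. Protocol 2.1 explains that the drug was approved in China without safety or efficacy data in Chinese patients and that this study is the commitment to collect them. Protocol 2.2 says the incidence of non-infectious pneumonitis will be determined at the regulator's request.

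**How it is summarised.** SAP 5.4.2.1 states: "The overview of adverse events included the number and percentage of patients with the following AE". SAP 5.4.2.2 to 5.4.2.4 use the same measure for events by term and grade, the four groups of adverse events of special interest (AESIs), deaths and SAEs. SAP 5.1 sets frequency and percentage as the general rule for categorical data. None of these sections plans an interval. Protocol 10.5.3.2 plans incidence tables, and Protocol 10.4.4 gives no supportive analysis of the primary objective.

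**Secondary endpoints.** For OS, SAP 5.5.1 plans a 95% interval for the median and adds that "the survival probabilities and their 95% confidence intervals at different time points such as at Month 3 and Month 6 were also calculated". SAP 5.5.2 applies similar methods to PFS.

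**Sample size.** SAP section 4: "The sample size was determined based on feasibility rather than statistical considerations", and "approximately 60 patients are now planned to be enrolled after further communication with the Center for Drug Evaluation".

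**Risk window and exposure.** Events are counted from first dose to 30 days after last dose (SAP 5.4.2; Protocol 10.5.3.1). Treatment is open-ended (Protocol 6.1.4). In SAP 5.4.1, "Patients with a certain duration of exposure" are summarised in bands from under 12 weeks to 84 weeks or more, separately from the adverse event tables.

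**The concern.** The study exists to estimate how often adverse events occur in this population, and those estimates are the only listed endpoints without a stated measure of uncertainty. This matters most for uncommon events. A zero or very small count of pneumonitis in a licence-renewal submission could be taken as reassurance when the data are still compatible with a rate of several percent. Because the sample size was set by feasibility, nothing elsewhere in the plan tells a reader what precision to expect.

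**Working it through.** **1. Can the planned size be tied to a precision?** Protocol 10.8 gives 6 to 10 new diagnoses per site per year, 5 sites, and "about 10% to 20% of diagnosed patients will be eligible and agree to participate the study".

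- Lowest accrual: 5 × 6 × 0.10 = 3 patients per year.
- Highest accrual: 5 × 10 × 0.20 = 10 patients per year.
- SAP section 4 allows up to 10 sites, which raises the highest figure to 10 × 10 × 0.20 = 20.

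These are accrual rates. They do not yield 60, and they carry no alpha, power or target interval width. The planned size therefore cannot be reproduced as a precision calculation, and no such calculation is claimed.

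**2. What interval does each percentage carry?** The exact 95% limits for x events in n patients are:

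- lower = 0.025 quantile of Beta(x, n − x + 1), or 0 if x = 0;
- upper = 0.975 quantile of Beta(x + 1, n − x).

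For x = 0 the upper limit reduces to 1 − 0.025^(1/n):

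- n = 60: 1 − 0.025^(1/60) = 6.0%
- n = 30: 1 − 0.025^(1/30) = 11.6%

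| Events / n | Reported under the plan | Exact 95% interval |
|---|---|---|
| 0/60 | 0% | 0 to 6.0% |
| 1/60 | 1.7% | 0.0 to 8.9% |
| 3/60 | 5.0% | 1.0 to 13.9% |
| 6/60 | 10.0% | 3.8 to 20.5% |
| 12/60 | 20.0% | 10.8 to 32.3% |
| 30/60 | 50.0% | 36.8 to 63.2% |
| 32/60 | 53.3% | 40.0 to 66.3% |
| 0/30 | 0% | 0 to 11.6% |
| 3/30 | 10.0% | 2.1 to 26.5% |
| 15/30 | 50.0% | 31.3 to 68.7% |

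The n = 30 rows correspond to the first interim (Protocol 10.7). The 32/60 row is close to the 53.9% stomatitis rate that Protocol 1.2.1.2 quotes from the global phase III pNET study. Even for a common event, the interval is about 26 points wide.

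**3. How easily could a real risk go unseen?** The chance of at least one case in 60 patients is 1 − (1 − p)^60. This is 45% for a true risk of 1%, 70% for 2% and 95% for 5%. An event with a true 2% risk would thus be missed altogether about 30% of the time.

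**4. Is there a time element?** The risk window is defined, but its length depends on each patient's last dose. At an interim it is cut short for patients still on drug. Exposure is described in its own tables and is not used as a denominator for adverse events. SAP Table 1 assigns an event with an incomplete onset date to a period but does not impute a date, so time to first event cannot be computed for such events under the present rules.

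**The case against.** The strongest reply is that the plan does what it says it will do. SAP 5.1 states: "The analytical method of this study was predominantly descriptive, without predetermined hypothesis test". The protocol promises descriptive safety statistics, no threshold or comparison is set for any adverse event, and n (%) is the usual format for safety tables. Anyone with the counts can calculate exact limits. The table templates are in a separate document (SAP section 8) that is not available here.

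Part of this stands. The SAP agrees with the protocol, and nothing here is invalid. But an interval needs no hypothesis, and the same descriptive SAP specifies intervals for OS and PFS. The usual format suits the many rows by preferred term; it serves less well for the few numbers that are the primary result. Templates should implement the SAP, and the SAP text asks for no interval.

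A reader might go further and infer three things that the documents do not support:

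- **That exposure is known to be very unequal.** Open-ended treatment makes variation likely, but the bands in SAP 5.4.1 are reporting categories, and no exposure data from this study are given.
- **That incidence has no time base.** It is tied to a defined on-treatment window, although the length of that window varies by patient.
- **That crude percentages from different data cuts cannot be compared.** No such comparison is planned. The interims are snapshots for licence renewal, and the external rates quoted in the protocol are themselves crude percentages.

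A rate per patient-year also has limits of its own. It summarises risk well only if the hazard is roughly constant, which the documents do not establish, and it needs the missing onset-date rule.

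**Conclusion.** The point holds as a gap in how precisely the primary result is reported. At the planned size, a zero count leaves rates up to 6.0% open (11.6% at about 30 patients), and a 10% incidence is compatible with anything from 3.8% to 20.5%. Under the present text these figures would appear as bare percentages. The limits assume 60 and 30 patients in the safety set and independent patients; the protocol says actual enrolment may differ. The change should be made, since it alters what a zero or small count can support. It would not alter the counts themselves, and it does not imply that the design is underpowered or that the crude percentages are wrong. Differing window lengths justify an optional supportive display and nothing stronger.

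**What to change.** **Main change.** In SAP 5.4.2.1 and 5.4.2.3, add exact (Clopper-Pearson) two-sided 95% intervals to:

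- the four headline incidences: treatment-emergent AEs, suspected-related AEs, Grade 3/4 AEs and SAEs;
- each AESI group: non-infectious pneumonitis, stomatitis/oral mucositis, hepatitis B reactivation, and cardiac failure or decreased ejection fraction.

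State that the intervals are descriptive. They are not needed for every preferred term. The cost is one extra column in existing tables, with no new data. Results for rare events will look less certain, which is accurate.

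**Optional support, AESIs only.** Because on-treatment windows differ in length and are cut short at the interims for patients still on drug, show one of the following:

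- patients with a first event per patient-year at risk; or
- the cumulative incidence of first event, with end of the on-treatment period and death as competing events.

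Either needs a stated rule for incomplete onset dates, which SAP Table 1 does not supply, so this part costs some extra specification and programming.

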2.4 Secondary study endpoints

- Overall Survival (OS): defined as time from the start of study treatment to death due to any cause;
- Progression Free Survival (PFS): defined as time from the start of study treatment to progression or death due to any cause.

3 Study design

This is an open-label, multi-center, single-arm study of the safety and efficacy of Afinitor in adult patients with locally advanced, well differentiated progressive pNET in China.

Patient who are eligible will be provided with everolimus by sponsor to treat pancreatic neuroendocrine tumors and will follow the visit schedule in Appendix 1 Visit Evaluation Schedule to collect safety and efficacy data until disease progression, unacceptable toxicity, death, visit deviation or other reason that may lead to discontinuation before the end of study.

All patients will be followed-up for survival status every 6 months by the investigator until death, lost to follow-up, withdrawal of consent for survival or end of study.

4 Sample size calculation

The sample size was determined based on feasibility rather than statistical considerations.

Based on pre-marketing field survey, each year, approximately 6 to 10 patients at each of the 5 to 10 study sites selected for this study will be newly diagnosed as ‘locally advanced or metastatic, well differentiated pancreatic neuroendocrine tumor’, about 10% to 20% of diagnosed patients will be eligible and agree to participate the study. Approximately 30 patients were initially planned to be enrolled, and approximately 60 patients are now planned to be enrolled after further communication with the Center for Drug Evaluation. Due to the uncertainties during the enrollment, the actual number of patients may differ from estimations.

5 Statistical Analysis

